6.1.2. All TEAEs

- Incidence of TEAEs by MedDRA SOC and preferred term
- Exposure-adjusted analysis of selected TEAEs;
- Incidence of TEAEs by number of years of treatment, MedDRA system-organ class and preferred term;

6.1.3. Toxicity Grade 3 or 4 TEAEs

- Incidence of toxicity Grade 3 or 4 TEAEs, by MedDRA SOC and preferred term
- Exposure-adjusted analysis of selected Grade 3 or higher TEAEs;
- List of subjects with any toxicity Grade 3 or 4 TEAEs

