### **11.3 Safety Analyses**

Adverse events, deaths, and safety-related laboratory tests will be summarized as follows:

- Incidence of all AEs
- Incidence of Grade 3 or higher AEs
- Incidence of SAEs
- Incidence of AEs and SAEs reasonably related to siltuximab
- Incidence of clinically important changes in safety-related laboratory parameters
- Incidence of deaths and malignancies
- Incidence of antibodies to siltuximab

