6.1.4. Siltuximab Treatment-Related TEAEs

- Incidence of TEAEs considered by the investigator to be related to siltuximab treatment, by MedDRA SOC, preferred term
- Incidence of TEAEs with toxicity Grade 3 or higher considered by the investigator to be related to siltuximab treatment, by MedDRA SOC and preferred term

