6.1.6. TEAEs Leading to Siltuximab Dose Delays

Siltuximab dose delays were not collected in parent study of C0328T03, therefore, the incidence of TEAEs leading to siltuximab dose delays during the long-term safety extension study will be summarized by MedDRA SOC and preferred term. The summaries will be presented by all grades and grade 3 or higher.

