6.1.7. TEAEs Leading to Discontinuation of Siltuximab Treatment

A summary of number of subjects who discontinued siltuximab treatment because of 1 or more TEAEs by MedDRA system-organ class and preferred term will be provided. The summaries will be presented by all Grades and Grade 3 or higher. This table includes associated TEAEs for those subjects who discontinued siltuximab treatment due to an adverse event reported on the “End of Treatment” CRF page.

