6.3. Adverse Events of Clinical Interest

6.3.1. Infusion-Related Reactions (IRR)

Number of subjects with any IRR associated with siltuximab administration during the long-term extension study will be summarized by MedDRA system-organ class and preferred term. Note that IRR was not collected in parent study C0328T03.

A listing of subjects with Grade 3 or higher treatment-emergent infusion-related reactions associate with siltuximab administration will be provided.

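### SAP 6.1.3 and 6.3.2 cap severe events at Grade 4 where Protocol 11.3 plans Grade 3 or higher, and the malignancy incidence in Protocol 11.3 becomes a listing only

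*SAP*

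**What the plan says.** **Severity threshold.** Protocol 11.3 lists "Incidence of Grade 3 or higher AEs" among the safety summaries, and the synopsis uses the same cut. Protocol 12.1.3 grades severity on a scale that runs to Grade 5, a death related to the event.

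SAP 6.1.3 has three outputs:
- a table: "Incidence of toxicity Grade 3 or 4 TEAEs, by MedDRA SOC and preferred term"
- an exposure-adjusted analysis: "Exposure-adjusted analysis of selected Grade 3 or higher TEAEs"
- a listing: "List of subjects with any toxicity Grade 3 or 4 TEAEs"

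The infection summary in SAP 6.3.2 is also restricted to Grades 3 and 4. The other severity-restricted outputs are not:
- 6.1.4: "Incidence of TEAEs with toxicity Grade 3 or higher considered by the investigator to be related to siltuximab treatment"
- 6.1.6 (dose delays): "The summaries will be presented by all grades and grade 3 or higher"
- 6.1.7 (discontinuations): "The summaries will be presented by all Grades and Grade 3 or higher"
- 6.3.1 (infusion-related reactions): "A listing of subjects with Grade 3 or higher treatment-emergent infusion-related reactions"

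**Malignancies.** Protocol 11.3 puts deaths and malignancies on one line, as incidences. SAP 6.2.1 tabulates all deaths. SAP 6.3.3 gives malignancies a subject listing, with no count, percentage or rate. Protocol 3.1 and 10.2 keep collecting malignancies after treatment stops, up to the 6-year data cutoff.

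**The concern.** Long-term safety is the primary objective, and in a descriptive single-arm study these tables are its evidence.

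With two severity thresholds, the outputs cannot be read against each other. The related subset of a term can show more subjects than the all-cause table that should contain it. Within 6.1.3, the incidence table and the exposure-adjusted analysis can report different numbers of subjects for the same term. Serious infection is a named risk in Protocol 1.2, yet the table devoted to infections would leave out the fatal ones.

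For malignancies, collection continues after treatment, but the SAP plans no table giving the incidence that Protocol 11.3 calls for.

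**Working it through.** The plan states no figure to reproduce on this point. The check sets the sections side by side and then gauges the size.

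**1. Where a Grade 5 event is counted, as the SAP is written**

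| SAP output | Grades covered | Grade 5 counted? |
|---|---|---|
| 6.1.1 overview | maximum grade 1 to 5 | yes |
| 6.1.2 all TEAEs by SOC and preferred term | all | yes |
| 6.1.3 table and listing | 3 or 4 | **no** |
| 6.1.3 exposure-adjusted, selected terms | 3 or higher | yes |
| 6.1.4 related, severe | 3 or higher | yes |
| 6.1.5 serious TEAEs | all | yes |
| 6.1.6, 6.1.7 and 6.3.1 | 3 or higher | yes, where it applies |
| 6.2.2 deaths due to TEAEs | outcome death or Grade 5 | yes |
| 6.3.2 infections | 3 or 4 | **no** |

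SAP 6.1 also says in general terms that TEAEs are summarized by toxicity grade. The specific list that follows contains no all-cause Grade 3 or higher table by SOC and preferred term.

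**2. Consequence for one preferred term.** Take one subject with a related fatal event and no Grade 3 or 4 record of that term, and no other subject with the term. The 6.1.4 count is 1 and the 6.1.3 count is 0, so related exceeds all-cause.

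**3. Size of the 6.1.3 shortfall.** Input: N = 75, the maximum in Protocol 11.2, all assumed treated. The shortfall is k/75, where k is the number of subjects whose only severe event is Grade 5. The documents do not give k, so a range is shown.
- k = 1: 1/75 = 1.3 percentage points
- k = 2: 2/75 = 2.7 points
- k = 3: 3/75 = 4.0 points
- k = 0: no difference

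**4. Malignancies outside the TEAE window.** Protocol 12.2.1 ends AE reporting 30 days after the last dose. SAP 6.1 closes the TEAE window then, or on the day before subsequent therapy if that is earlier; events judged drug-related count whatever their date. A malignancy judged unrelated and found later is therefore in the 6.3.3 listing but in no malignancy or TEAE incidence. If fatal, it can appear as a cause of death in 6.2.1, which counts deaths rather than malignancies.

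To show how much collection time this can involve, assume a subject with six years in the extension, no subsequent therapy within the 30 days, and malignancy collection throughout.

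Coverage = (years on treatment × 365.25 + 30) / (6 × 365.25)

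| Assumed split | Covered by TEAE window | Not covered | 30 days as share of off-treatment time |
|---|---|---|---|
| 5 years on, 1 off | 1856.25/2191.5 = 84.7% | 15.3% | 30/365.25 = 8.2% |
| 3 on, 3 off | 1125.75/2191.5 = 51.4% | 48.6% | 30/1095.75 = 2.7% |
| 1 on, 5 off | 395.25/2191.5 = 18.0% | 82.0% | 30/1826.25 = 1.6% |

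These are shares of time, not of malignancies. Earlier subsequent therapy would lower the coverage; counting parent-study exposure would raise it.

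**The case against.** The strongest reply is that nothing disappears. The line in Protocol 11.3 does not mention SOC or preferred term, and the overall Grade 3 or higher figure follows from the maximum-grade categories in SAP 6.1.1. Fatal TEAEs have their own table in 6.2.2 by preferred term and relationship, the same dimensions as the infection table. Showing Grade 3 to 4 events and fatal events separately is a defensible layout. The 6.3.3 listing is not limited to the TEAE window, so with at most 75 subjects the malignancies can be counted by hand. The time splits above are assumed, and they give every subject six extension years although the cutoff runs from the first enrollment.

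Much of this stands. It means that events are separated rather than lost, and that the time shares are only illustrative. It does not rescue the layout. A deliberate split would not put both thresholds in the three outputs of 6.1.3, nor keep Grade 5 in the related-event table. That related can exceed all-cause is conditional on such an event occurring, but the tables should be specified so that it cannot happen. A listing that the reader must count is not the incidence the protocol plans. It is also fair that a malignancy count needs a rule on recurrences; the listing already carries a flag for them.

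**Conclusion.** The concern holds on both parts. The table and listing in SAP 6.1.3 and the infection table in 6.3.2 depart from Protocol 11.3 and from the rest of the SAP, and 6.3.3 has no counterpart to the protocol's malignancy incidence.

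The effect on the 6.1.3 total is 1.3 points per affected subject if 75 are treated, and nil if no subject has Grade 5 as the only severe event. The effect on internal consistency can arise from a single related fatal event. The malignancy gap is confined to cases judged unrelated and found after the TEAE window; the exposed share of collection time depends on how long subjects are followed off treatment, which the documents do not give.

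No hypothesis test or decision rule is affected. The correction should still be made, because these outputs serve the primary objective.

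**What to change.** 1. In SAP 6.1.3, change the heading, the incidence table and the listing from Grade 3 or 4 to Grade 3 or higher. Make the same change in 6.3.2. The fatal-event table in 6.2.2 stays as it is.
2. In SAP 6.3.3, keep the listing and add the number and percentage of subjects in the safety population with a malignancy over all follow-up, to last contact or the 6-year cutoff. State when the period starts, whether parent-study cases count, and whether recurrences count, using the existing recurrence flag. A rate per patient-time is optional.

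The cost is a wording change in two SAP sections and one added summary line, from AE and follow-up data already collected.

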6.1.4. Siltuximab Treatment-Related TEAEs

- Incidence of TEAEs considered by the investigator to be related to siltuximab treatment, by MedDRA SOC, preferred term
- Incidence of TEAEs with toxicity Grade 3 or higher considered by the investigator to be related to siltuximab treatment, by MedDRA SOC and preferred term

6.1.5. Serious Adverse Events (SAEs)

- Incidence of treatment-emergent SAEs, by MedDRA SOC and preferred term
- Incidence of treatment-emergent SAEs considered by the investigator to be related to siltuximab treatment, by MedDRA SOC, preferred term
- List of subjects with any treatment-emergent SAEs

6.1.6. TEAEs Leading to Siltuximab Dose Delays

Siltuximab dose delays were not collected in parent study of C0328T03, therefore, the incidence of TEAEs leading to siltuximab dose delays during the long-term safety extension study will be summarized by MedDRA SOC and preferred term. The summaries will be presented by all grades and grade 3 or higher.

6.1.7. TEAEs Leading to Discontinuation of Siltuximab Treatment

A summary of number of subjects who discontinued siltuximab treatment because of 1 or more TEAEs by MedDRA system-organ class and preferred term will be provided. The summaries will be presented by all Grades and Grade 3 or higher. This table includes associated TEAEs for those subjects who discontinued siltuximab treatment due to an adverse event reported on the “End of Treatment” CRF page.

6.2. Deaths

6.2.1. All Deaths

A summary of all deaths and cause of death for the safety population will be tabulated. The primary cause of death collected on CRF page will be reported. The similar summaries will be presented for subjects who died within 30 days of last siltuximab treatment dose.

6.2.2. Death Due to TEAEs

The number of subjects who died due to TEAEs will be summarized by preferred term and relationship to study siltuximab treatment. The TEAEs included in this table are AEs with outcome death or toxicity Grade 5 recorded in the AE CRF page.

A listing of subjects who died due to treatment-emergent adverse events will be provided.

6.3. Adverse Events of Clinical Interest

6.3.1. Infusion-Related Reactions (IRR)

Number of subjects with any IRR associated with siltuximab administration during the long-term extension study will be summarized by MedDRA system-organ class and preferred term. Note that IRR was not collected in parent study C0328T03.

A listing of subjects with Grade 3 or higher treatment-emergent infusion-related reactions associate with siltuximab administration will be provided.

6.3.2. Infections and Infestations

A summary of number of subjects with 1 or more toxicity Grade 3 or 4 treatment-emergent infections and infestations by MedDRA preferred term and relationship to siltuximab treatment will be provided.

6.3.3. Secondary Malignancies

A listing of subjects who reported secondary malignancies during the study will be provided. The listing will include subject ID, diagnosis, study day of diagnosis, recurrence of a prior existing malignancy (yes, no) and stage of disease etc. information whenever a second primary malignancy is observed. In addition, treatment related to secondary malignancy, a total of siltuximab dose received, whether or not subject received subsequent MCD therapy information will also be presented in the listing.

6.4. Clinical Laboratory Tests

Safety evaluation of clinical laboratory tests will focus on the following selected laboratory analytes based on long-term safety extension study.

- Hematology panel: hemoglobin, platelet count, white blood cell (WBC) count with absolute neutrophils and lymphocytes
- Blood chemistry panel: sodium, potassium, creatinine, glucose, aspartate aminotransferase (AST), alanine aminotransferase (ALT), total bilirubin, alkaline phosphatase, uric acid, creatinine, phosphate and albumin.
- Lipid panel: cholesterol, triglycerides, HDL and LDL

Blood samples for serum hematology and biochemistry were taken at the screening visit, every cycle in 1st year for siltuximab-naïve subjects, every 3 cycles for 3-week regimen and every other administration visit at a minimum for those on 6-week regimen.

Descriptive statistics (mean, standard deviation, median, range) will be used to summarize observed laboratory values and change from baseline in observed value at each scheduled visit. Line plot of mean with SE for each laboratory analyte over time up to 6 years will be displayed for hematological parameters: hemoglobin, neutrophils, platelets, WBC, and biochemistry parameters: AST, ALT, creatinine, albumin, bilirubin, HDL, LDL, cholesterol, and triglycerides.

The worst toxicity grade in hematology and chemistry during siltuximab treatment will be summarized by toxicity grade. Shift tables from baseline to worst toxicity grade during siltuximab treatment will be provided for each laboratory analyte listed above. These tables will summarize the number of subjects with each baseline CTC grade and changes to the maximum CTC grade.

6.5. Vital Signs and ECG Findings

In the long-term safety extension study, vital signs (temperature, blood pressure, and heart rate) will be measured predose and end of siltuximab infusion on Day 1 of Cycle 1. Thereafter, vital signs will be measured only before each siltuximab administration on Day 1 of each cycle, and as clinically indicated.

The observed values in vital signs and change from baseline in observed value at each scheduled visit will be descriptively summarized.

Similar summaries will be provided for weight at each assessment visit.

A listing of ECG findings will be provided for siltuximab-naïve subjects who enrolled into extension study.

6.6. Other Safety Assessment

Baseline chest X-ray is required within 3 months of first dose within this study and annually thereafter. If equivalent imaging (ie, CT, MRI) was performed for routine medical care at these timepoints, then it is allowed instead of a chest X-ray.

A listing of chest X-Ray or equivalent imaging results during long-term safety extension study will be provided.

7. IMMUNOGENICITY

7.1. Sampling Timepoints

Blood samples to determine antibodies to siltuximab will be collected from all subjects in the long-term safety extension study every 12 weeks while receiving siltuximab in conjunction with a dosing visit, and at Week 4, Week 8, and Week 12 following the last administration of siltuximab.

In addition, a blood sample should be drawn, if possible, to determine antibodies to siltuximab any time an infusion related reaction is observed or reported during the study. This sample should be obtained as soon as possible after the reaction.

7.2. Analysis Methods

Immunogenicity samples will be analyzed at the 6-year data cutoff. Immunogenicity analysis will be based on long-term safety extension study. The incidence of antibodies to siltuximab (immunogenicity) will be summarized for all subjects who receive a dose of siltuximab and have appropriate samples for detection of antibodies to siltuximab. In addition, subjects who are positive for antibodies to siltuximab will also be listed.
